Nervous system disorders / Dizziness	10%
Psychiatric disorders / Insomnia	10%
Vascular disorders / Thromboembolic event	10%
Grade 5 Toxicities (Treatment Related + Not Related):	0%
Grade 4 Toxicities (Treatment Related + Not Related):	
Blood and lymphatic system disorders / Anemia	5%
Investigations / Platelet count decreased	5%
Investigations / Lymphocyte count decreased	5%
Metabolism and nutrition disorders / Hypokalemia	5%
Metabolism and nutrition disorders / Hyperglycemia	5%
Metabolism and nutrition disorders / Hypoalbuminemia	5%
Investigations / Neutrophil count decreased	5%
Infections and infestations / Sepsis	5%
Grade 3 Toxicities (Treatment Related + Not Related) Occurring ≥10% Patients:	
Metabolism and nutrition disorders / Hyperglycemia	45%
Investigations / Lymphocyte count decreased	30%
Metabolism and nutrition disorders / Hypokalemia	30%
Gastrointestinal disorders / Diarrhea	25%
Metabolism and nutrition disorders / Hyponatremia	25%
Nervous system disorders / Peripheral sensory neuropathy	25%
Vascular disorders / Thromboembolic event	25%
Blood and lymphatic system disorders / Anemia	20%
Investigations / Neutrophil count decreased	20%
Vascular disorders / Hypertension	20%
Gastrointestinal disorders / Abdominal pain	20%
Investigations / Platelet count decreased	15%
General disorders and administration sit / Fatigue	15%
Metabolism and nutrition disorders / Dehydration	15%
Gastrointestinal disorders / Vomiting	15%
Blood and lymphatic system disorders / Leukocytosis	15%
Metabolism and nutrition disorders / Hypophosphatemia	15%

Gastrointestinal disorders / Nausea	10%
Cardiac disorders / Cardiac disorders - Other	10%
Respiratory, thoracic and mediastinal di / Dyspnea	10%
Infections and infestations / Enterocolitis infectious	10%
Infections and infestations / Lung infection	10%
Respiratory, thoracic and mediastinal di / Hypoxia	10%

*% of patients unless otherwise specified; **Adverse events considered by the investigator to be related (probably or possibly related) to study drug treatment in combination [related here refers to combination of both devimistat and mFFX (not devimistat alone)]

Table 6 Clinical Experience of CPI-613[®] (devimistat) in Solid Tumors and Hematological Malignancies

N o.	Trial ID, NCT ID, US FDA IND No.	Phase	Indication	Treatment Detail	#Dosed	#Evaluated for Efficacy	#Evaluated for Safety	Efficacy Summary	Recruitment Status	Result (Interim/Final)	
										Efficacy	Safety

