5.3.1. Discontinuation of Treatment

The Investigator must protect the subject's welfare and may discontinue any study treatment at any time when this action appears to be in the subject's best interest. The reason for the subject's discontinuation must be recorded in the subject's electronic case report. Possible reasons for the discontinuation may include, but are not limited to, the following:

- Disease Progression defined as follow: disease progression documented by CT scan (or MRI) based on RECIST version 1.1 criteria, as determined in the protocol;
- Adverse Event;
- Any significant Protocol Violation as per protocol;
- Withdrawal of consent by an enrolled subject.

5.3.1.1 Patients requiring delay for more than 3 weeks because of toxicity.

- 5.3.1.2 Unacceptable toxicity from FFX or mFFX + devimistat (Grade 3 or more severity of toxicity).
- 5.3.1.3 The subject becomes pregnant (treatment should be discontinued immediately)
Intercurrent illness with a condition, injury, or disease unrelated to the intended disease for which the study is investigating, that renders continuing the treatment unsafe or regular follow-up impossible.
- 5.3.1.4 General or specific changes in the patient's condition that in the opinion of the treating physician renders the patient ineligible for further investigational treatment.
- 5.3.1.5 Recurrent grade 4 adverse events despite all appropriate dose reductions.
- 5.3.1.6 Non-compliance with investigational treatment, protocol-required evaluations or follow-up visits.
- 5.3.1.7 Other reasons as determined by the Investigator or Sponsor: A subject may have study treatment discontinued if, in the opinion of the Investigator or Sponsor, it is not in the subject's best interest to continue; Unambiguous clinical progression documented by the Investigator in the absence of radiological confirmation.

Subjects who discontinue all study medication for any reason should remain in the study for long-term follow up assessments unless they withdraw informed consent, die, or become lost to follow up. Long-term follow up evaluations will be performed accordingly as described in the protocol. In the event of study treatment discontinuation, the subject should be instructed to report to the site as early as possible after the decision to discontinue study treatment has been made. All End of Treatment procedures should be performed according to the protocol.

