8.3. Time Period and Frequency for Event Assessment and Follow-Up

The occurrence of an AE or SAE may come to the attention of study personnel during study visits and interviews of a study participant presenting for medical care, or upon review by a study monitor. All AEs including local and systemic reactions not meeting the criteria for SAEs will be captured in the CRF. Information to be collected includes event description, time of onset, clinician's assessment of severity, relationship to study product (assessed only by those with the training and authority to make a diagnosis), and time of resolution/stabilization of the event. All AEs occurring while on study must be documented appropriately regardless of relationship, action taken with study drug (drug withdrawn, dose reduced), other treatment for AE (drug therapy, other procedure) and outcome of AE. All AEs will be followed to adequate resolution (return to baseline).

Any medical condition that is present at the time that the participant is screened will be considered as baseline and not reported as an AE. However, if the study participant's condition deteriorates at any time during the study, it will be recorded as an AE. UPs will be recorded in the data collection system throughout the study.

Changes in the severity of an AE will be documented to allow an assessment of the duration of the event at each level of severity to be performed. AEs characterized as intermittent require documentation of onset and duration of each episode. Disease progression will not be considered as an AE/SAE.

The PI will record all reportable events with start dates occurring any time after informed

consent is obtained until 7 (for non-serious AEs) or 30 days (for SAEs) after the last dose of the study drug. At each study visit, the investigator will inquire about the occurrence of AE/SAEs since the last visit. Events will be followed for outcome information until resolution or stabilization.

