9.4.4. Safety Analyses

The assessment of safety will be based mainly on the frequency of adverse events based on the Common Terminology Criteria for Adverse Events (CTCAE version 4) grade. Adverse events will be coded according to MedDRA, current version. The safety outcomes will include the occurrence of at least one serious adverse event, of at least one grade 3/4 adverse event, and of at least one adverse event requiring the discontinuation of study treatment.

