6.3.3 Safety Analyses

The assessment of safety will be based mainly on the frequency of adverse events based on the Cancer Therapy Evaluation Program (CTEP) Active Version of the NCI Common Terminology Criteria for Adverse Events (CTCAE 4.0) grade. The CTEP Active Version of the CTCAE is identified and located on the [CTEP website](#). If the severity or intensity is not specifically graded by the guidance document from CTEP, the site investigators have been instructed in the protocol to revert to the general definitions of grade 1 through grade 5 shown in the table below. Additional information about adverse event or unanticipated problem reporting can be found in the protocol, section 8.

Severity	Description
Grade 1	Mild; events require minimal or no treatment and do not interfere with the participant's daily activities.
Grade 2	Moderate; events result in a low level of inconvenience or concern with the therapeutic measures. Moderate events may cause some interference with functioning.
Grade 3	Severe; events interrupt a participant's usual daily activity and may require systemic drug therapy or other treatment.
Grade 4	Life threatening or disabling; patient at risk of death at the time of the event.

Confidential

Grade 5	Death related to AE.
---------	----------------------

The following tabular summaries of adverse events will be provided using the safety population:

- All AEs by SOC and CTCAE term, by treatment arm and overall
- Patients with at least one AE by SOC and CTCAE term, by treatment arm and overall
- Patients with at least one AE by relatedness, by treatment arm and overall
- Patients with at least one AE by severity, by treatment arm and overall
- All serious AEs (SAEs) by SOC and CTCAE term, by treatment arm and overall
- Patients with at least one SAE by SOC and CTCAE term, by treatment arm and overall
- Patients with at least one AE that led to a change in study medication (e.g., dose modification, interruption, or permanent discontinuation), by treatment arm and overall
- Patients with at least one AE requiring a change in concomitant therapy (e.g., addition, interruption, discontinuation, or change in a concomitant medication, therapy, or treatment), by treatment arm and overall.

Adverse events that are still ongoing at the time of data cut-off should not be included in any of the tables described above. Instead, a separate table should be presented containing all on-going AEs by SOC and CTCAE term, by treatment arm and overall.

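### SAP 6.3.3 leaves adverse events ongoing at data cut-off out of all eight main AE tables, and lists no table of CTCAE term by grade

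*SAP*

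**What the plan says.** SAP 6.3.3 lists eight tables on the safety population, each by arm and overall:

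1. all AEs by SOC and CTCAE term
2. patients with an AE by SOC and term
3. patients with an AE by relatedness
4. patients with an AE by severity
5. all SAEs by SOC and term
6. patients with an SAE by SOC and term
7. patients with an AE that changed study medication (dose change, interruption or permanent discontinuation)
8. patients with an AE that changed concomitant therapy

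It then says: "Adverse events that are still ongoing at the time of data cut-off should not be included in any of the tables described above". The excluded events are reported in one further table, split by arm, which the SAP describes in these words: "a separate table should be presented containing all on-going AEs by SOC and CTCAE term".

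Grade enters through one line, "Patients with at least one AE by severity, by treatment arm and overall". Term enters through lines such as "Patients with at least one AE by SOC and CTCAE term, by treatment arm and overall". The same section opens by saying that safety will rest mainly on AE frequency by CTCAE 4.0 grade.

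Protocol 9.4.4 names three safety outcomes: the occurrence of at least one SAE, "of at least one grade 3/4 adverse event", and of at least one AE that requires stopping study treatment. It makes no exception for unresolved events.

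**The concern.** Whether an AE occurred and whether it has ended by the cut-off are different questions. The exclusion makes the answer to the first depend on the second. It reaches exactly the tables that would deliver the Protocol 9.4.4 outcomes: SAEs, severity and change in study medication.

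The second gap is separate. The arms differ in chemotherapy dose: oxaliplatin 65 vs 85 mg/m² and irinotecan 140 vs 180 mg/m² (Protocol Tables 7 and 8). Protocol 2.1.2 says modified dosing reduces neuropathy, diarrhea and neutropenia. Whether the experimental arm has less severe toxicity of these kinds is an obvious safety question, and answering it needs term and grade in the same table. The sponsor's own phase I summary (Protocol Table 5) has such a block, headed "Grade 3 Toxicities (Treatment Related + Not Related) Occurring ≥10% Patients". The tables listed in SAP 6.3.3 could not be set beside it.

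**Working it through.** The plan states no figure on this point, so there is nothing to reproduce. The check compares the two documents, with short illustrations.

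**Step 1. Protocol outcomes against SAP tables.**

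| Protocol 9.4.4 outcome | SAP 6.3.3 table that covers it | Ongoing AEs counted? | Recoverable from the ongoing-AE table? |
|---|---|---|---|
| At least one SAE | Patients with an SAE by SOC and term | No | No: seriousness not shown |
| At least one grade 3/4 AE | Patients by severity | No | No: grade not shown |
| At least one AE requiring discontinuation | Patients with an AE that changed study medication | No | No: action taken not shown |

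**Step 2. Can the two sets of tables be added?** The ongoing-AE table is worded as AEs, not patients. Even if it counted patients, the overlap would be unknown. With share a in the main table and b in the ongoing table, the share with at least one event lies between max(a, b) and min(1, a + b). For a = 50% and b = 30% that is anywhere from 50% to 80%.

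**Step 3. Size of the undercount.** Let p be the true share of patients with a given event and o the share of those cases ongoing at cut-off. With one such event per affected patient, the table shows p × (1 − o). For p, take the phase I grade 3 sensory neuropathy rate of 5/18 = 28% (Protocol Appendix III). The documents do not give o, so a range is assumed.

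| o | Shown rate | Of 250 patients (true count 70) |
|---|---|---|
| 10% | 0.28 × 0.9 = 25.2% | 63 |
| 30% | 0.28 × 0.7 = 19.6% | 49 |
| 50% | 0.28 × 0.5 = 14.0% | 35 |

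A patient with several qualifying events drops out only if all of them are ongoing, so the loss is then smaller. It is never negative, so the tables cannot overstate.

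**Step 4. Difference between arms.** If 28% is true in both arms and 30% of cases are ongoing in one arm against 50% in the other, the tables show 19.6% vs 14.0%. Exchanging the two shares reverses the sign.

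**Step 5. Term by grade.** Of the nine tables (eight plus the ongoing-AE table), five show term (1, 2, 5, 6 and the ongoing-AE table), one shows grade (4), and none shows both. The any-grade row is a poor substitute. In Appendix III, 17 of 18 patients had sensory neuropathy and 5 had grade 3, so (17 − 5)/17 = 71% of the cases in such a row were below grade 3.

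**The case against.** **In the plan's defense.** Ongoing events are not lost, since they appear by term and arm in their own table. SAP section 5 also promises listings, where noted, for data shown in tables. Protocol 8.3 mentions return to baseline but also allows follow-up to end once an event has stabilized, and it asks for changes in severity to be documented. Stable neuropathy might therefore receive an end date, and a grade 3 episode that eased might count as closed. Few events might then be ongoing.

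This limits the size but does not rescue the rule. The separate table lacks grade, seriousness, relatedness and action taken, and a listing is not a comparison by arm. If few events are ongoing, the exclusion also has little purpose.

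**Three stronger readings that the documents do not support.**

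- *Severe neuropathy or diarrhea is hidden altogether.* It is not. Closed serious events appear by term and arm in the SAE tables. What is missing is non-serious grade 3 events by term, and the grade label. SAP section 10, section 12 and the table shells are not in the text available, so the point covers only what 6.3.3 lists.
- *The rule favors the arm that lives longer.* Take the design medians (12 and 17.14 months), exponential survival, 500 patients, and uniform accrual over 18 to 33 months. About 27% of control and 39% of experimental patients are then alive at 335 deaths. With a true 25% in both arms and half the cases in living patients open, the tables show 0.25 × (1 − 0.135) = 21.6% vs 0.25 × (1 − 0.195) = 20.1%. If events still open at death are also coded ongoing, half open gives 12.5% in both arms and no tilt. If full-dose oxaliplatin leaves longer-lasting neuropathy, the tilt would favor control. Being alive is also a weak proxy for an open AE, because new non-serious AEs are recorded only until 7 days after the last dose. The direction is undetermined.
- *Pooling over terms must dilute a real difference.* With other grade 3/4 events at 70% in both arms and independent of the term, a true 25% vs 15% gives 77.5% vs 74.5%, or 3.0 points instead of 10. With other events at 70% vs 60%, the pooled rates are 1 − 0.30 × 0.75 = 77.5% and 1 − 0.40 × 0.85 = 66.0%, or 11.5 points. Dilution follows from the assumption, not from the documents.

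**Conclusion.** The exclusion is wrong as written and should be changed. That part is firm: it is an explicit instruction, and it conflicts with the outcomes in Protocol 9.4.4. What is certain is the direction within each main table, which can only undercount. The 25.2%, 19.6% and 14.0% are illustrations. They rest on one event per patient, a phase I rate from 18 patients and assumed ongoing shares, and they are not estimates for this trial. No bias toward either arm is shown.

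The missing cross of term and grade is a real but narrower gap. It concerns non-serious grade 3 events and the grade label, within the tables that 6.3.3 lists. It is held with less certainty, because parts of the SAP cannot be seen.

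**What to change.** In SAP 6.3.3, delete the exclusion sentence so that AEs ongoing at cut-off count in every AE table. Keep the ongoing-AE table as a supplement. Add one table of patients by SOC, CTCAE term and worst grade, by arm, with a column for grade 3 or higher and each patient counted once per term at the worst grade.

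The cost is one more table, from term, severity and resolution data that Protocol 8.3 already collects. The efficacy analyses are untouched. Reported AE rates will be higher than under the present rule.

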6.4 Exploratory Objectives

6.4.1 A β - data, or other important documents

These analyses fall outside of the scope of this SAP.

6.4.2 z, i z)

These analyses fall outside of the scope of this SAP.

6.5 Additional Analyses

Confidential

For a given cycle, a table will be provided displaying ECG data summarized by treatment arm, day, and timepoint using the safety population, if substantial data exists for Full or Sparse ECG. There will be a table for each cycle.

7. Study Patients

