2.3. Risk/Benefit Assessment

Please refer to the appendix III for study-specific assessment for details.

Primary Objective:

- To determine efficacy of devimistat plus mFFX compared to standard care FFX in terms of **Overall Survival (OS)**

Secondary Objectives:

- To determine efficacy of devimistat plus mFFX compared to standard care FFX in terms of **Progression-Free Survival (PFS)**.
- To determine efficacy of devimistat plus modified FOLFIRINOX (mFFX) compared to standard care FOLFIRINOX (FFX) in terms of **Objective Response Rate (ORR)**. ORR is defined as Complete Response (CR) plus Partial Response (PR).
- To evaluate **Duration of Response (DOR)**
- **Safety Analysis:** The assessment of safety will be based mainly on the frequency of adverse events based on the Common Terminology Criteria for Adverse Events (CTCAE version 4) grade. Adverse events will be coded according to MedDRA. The safety outcomes will include the occurrence of at least one serious adverse event, of at least one grade 3/4 adverse event, and of at least one adverse event requiring the discontinuation of study treatment. **QTc** intervals will be also evaluated as part of safety analysis.
- To assess **PK** of devimistat.
- To evaluate **Patient-Reported Outcomes (PRO)** for devimistat plus mFFX compared to standard care FFX.

Exploratory Objectives:

- To explore **biomarkers** using diagnostic biopsies and blood/plasma samples.
- To assess **PK/PD** of **dose/exposure-response** for devimistat on efficacy (e.g. PFS), safety (e.g. QTc) and exploratory biomarkers.

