4.2.2. Secondary Endpoints

This study has six secondary endpoints:

- **Progression-Free Survival (PFS)**, defined as the duration from the date of randomization to the date of progressive disease (assessed by an independent, blinded, central review) or death from any cause. PFS will be confirmed by investigator's assessment with the intent to perform sensitivity analyses.
- **Objective Response Rate (ORR)**, defined as the rate of Complete Response (CR) plus Partial Response (PR). A patient's best response within the first 12 cycles will be used for this determination, as assessed by independent, blinded, central review as per RECIST guideline version 1.1.¹⁸ ORR will be confirmed by investigator's assessment with the intent to perform sensitivity analyses.

- **Duration of Response (DOR)**
- **Safety: AEs, SAEs, QTc.**
- **Pharmacokinetics:** Full PK – C_{max} , T_{max} , AUC_{0-t} , AUC_{inf} , CL, V, $T_{1/2}$; Sparse PK – concentrations from Sparse PK sampling plus concentrations from Full PK sampling time points to be used for Population PK analysis
- **Patient-Reported Outcomes (PRO):** At baseline and day 1 of every even numbered cycle, patient will be required to complete one self-administered quality of life instrument.

NCCN-FACT FHSI-18 is a widely used PRO questionnaire for patients with hepatobiliary cancer (liver, bile duct and pancreas) developed by FACIT.org available at: <http://www.facit.org/FACITOrg/Questionnaires>. Summary statistics of the scores will be shown by cycle (pre and post treatment). Scores will be compared between standard and study arms. Efforts to avoid missing data will include data collection to be done during follow up clinic visits only and no additional visits will be required to complete the questionnaire. Additionally, only the validated, user friendly version of the questionnaire will be used for data collection.

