Cycle 1, Day 3	0 hr. ±15 (pre-dose) 0.25 hr. ±15 min 0.5 hr. ±15 min 1 hr. ±15 min 2 hr. ±15 min 2.5 hr. ±15 min 3 hr. ±15 min 4 hr. ±15 min 6 hr. ±15 min	Up to 24 patients above	Pre-infusion

B. Sparse ECG Measurement Schedule:

The remaining patients randomized to CPI-613® (devimistat) plus modified FFX (i.e. Arm 1) and all patients on FFX (i.e. Arm 2) will undergo a Sparse ECG analysis. 12-lead ECGs will be recorded at defined intervals. Subjects will be placed in a supine position for at least 10 minutes prior to timepoints for ECG recording. **This Sparse ECG measurement will be measured at a local ECG laboratory and confirmed by central read.** At each protocol-specified timepoint, QT and RR intervals will be measured from each of the three independent 12-lead ECG recordings (i.e., 3 replicates). The QTc interval will be derived using Fridericia's formula from the preceding RR interval and the QT interval in each beat and the median QTcF in each replicate will be calculated. The mean across medians from all replicates will be used as the subject's reportable value at that timepoint. All medications administered to subjects from 4 hours prior to the first ECG reading through all time points will be recorded (including doses and time of administration). Measurement of PR and QRS intervals will be performed semi-automatically on three sequential beats from each of the three replicates. The mean value will be

calculated for each replicate and then the mean of these used as the subject's reportable value at the timepoint (adapted from Darpo et. al.¹⁹). Time points for sparse ECG recordings are listed in Table 15 below.

Table 15 Sparse ECG measurement schedule.

Cycle #, Day #	Timepoints a = 5 min window between the ECG's	N	Comment on Assessment Timepoint
Cycle 1, Day 1	0 hr. (pre-dose) 0.25 hr. 0.5 hr.	Approx. 476 patients = Remaining 225 patients on Arm 1 + All 250 patients on Arm 2	Arm 1: Pre-devimistat infusion Arm 2: Pre-Oxaliplatin infusion
Cycle 1, Day 3	0 hr. (pre-dose) 0.25 hr. 0.5 hr.	Approx. 476 patients above	Arm 1: Pre-devimistat infusion Arm 2: Just prior to completion of 5-FU infusion
Cycle 2, Day 3	0 hr. (pre-dose) 0.25 hr. 0.5 hr.	Approx. 476 patients above	Arm 1: Pre-devimistat infusion Arm 2: Just prior to completion of 5-FU infusion
Cycle 3, Day 3	0 hr. (pre-dose) 0.25 hr. 0.5 hr.	Approx. 476 patients above	Arm 1: Pre-devimistat infusion Arm 2: Just prior to completion of 5-FU infusion

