4.4 ECG

The 24 patients receiving CPI-613 plus modified FFX (i.e., Arm 1) assigned to the full PK analysis sub-study will also undergo a full ECG analysis. 12-lead ECGs will be recorded at defined intervals from 30 minutes prior to dosing of CPI-613 on cycle 1, day 1 to 6 hours after dosing on day 1. Subjects will be placed in a supine position for at least 10 minutes prior to timepoints for ECG and PK sampling. ECG recordings will be taken immediately prior to PK sample draw at each time point. ECG intervals for this full ECG analysis will be measured at a central ECG laboratory, who will be fully blinded to timepoints and subject identification.

5. General Analysis Definitions

Data will be analyzed using SAS (version 9.4 or higher).

Descriptive statistics will be tabulated as follows:

- Categorical data will be summarized in contingency tables presenting frequencies and percentages.
- Continuous data will be summarized using number of non-missing values (n), mean, standard deviation, median (25th, 75th), minimum, and maximum values.

The baseline tables will be created by treatment arm and overall. Tables containing post-randomization information will be displayed by treatment arm, unless otherwise specified.

Listings with individual values will be provided for all data presented in the tables, where noted. The listings will be presented by identifiers, such as treatment group, center, and patient number.

Confidential

One-sided tests will be used at a significance level equal to 0.025. Two-sided confidence intervals will be computed for a coverage of 0.95.

Time-to-event analyses will be performed using the Kaplan-Meier method. Subjects who have not had the event of interest at the time of the analysis will be censored at the time of the last follow up. Summary statistics will be provided by treatment arm in terms of the number of events, number of censored observations, median, and 95% confidence interval, and survival probabilities at specific time points (such as 1 year, 2 years, etc.). Survival curves will be plotted by treatment arm and compared with a log-rank test stratified by performance status and tumor location. A stratified Cox regression model will be used to estimate the hazard ratio and its 95% CI, as well as to adjust the comparison for baseline covariates.

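### QTc is part of the secondary safety endpoint, but the only ECG output in the visible SAP is conditional and requires neither within-patient QTcF change nor a count of patients over a limit

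*SAP*

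**What the plan says.** **Protocol.** The secondary safety objective says that QTc "intervals will be also evaluated as part of safety analysis", and section 4.2.2 lists "Safety: AEs, SAEs, QTc" among the secondary endpoints. Section 7.1.1 sets out the measurement in detail: Fridericia correction, replicate recordings and one reportable figure per patient per timepoint ("The mean across medians from all replicates will be used as the" reportable value). There are two ECG sets:

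- **Full set:** up to 24 Arm 1 patients, nine timepoints on each of Cycle 1 Day 1 and Cycle 1 Day 3, read blinded at a central laboratory (Table 14).
- **Sparse set:** everyone else ("Remaining 225 patients on Arm 1 + All 250 patients on Arm 2"), three timepoints at each of seven visits in cycles 1, 2, 3, 6, 9 and 12 (Table 15). On reading: "This Sparse ECG measurement will be measured at a local ECG laboratory and confirmed by central read".

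Protocol section 9.4.4 names AE-based safety outcomes and no QTc analysis. Section 9.1 leaves the full methods to the SAP.

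**SAP.** Section 6.3.3 lists AE, SAE and death outputs. Section 4.4 describes the full ECG collection and names no output. Section 6.5 is the only visible ECG output: a table for each cycle, "summarized by treatment arm, day, and timepoint using the safety population, if substantial data exists for Full or Sparse ECG". Section 5 gives the statistics for continuous data as "number of non-missing values (n), mean, standard deviation, median (25th, 75th), minimum, and maximum values", and counts and percentages for categorical data. On listings it says: "Listings with individual values will be provided for all data presented in the tables, where noted". Section 5.6 defines baseline as the last non-missing assessment before treatment starts.

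**The concern.** The protocol puts considerable effort into one clean QTcF value per patient and timepoint, but the visible analysis plan does not oblige anyone to use those values patient by patient. Two things are at stake.

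- **The output can be dropped.** The table depends on an undefined judgement about whether there are enough data. In an open-label trial that judgement would be made by people who may have seen the data.
- **If produced, it may not answer the question.** A QTc safety review asks how far individual patients moved from their own baseline, and how many went past a level of concern. Summaries of ECG data by arm, day and timepoint need not answer either. A patient who entered with a high QTcF looks the same as one who rose on treatment.

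The protocol gives reasons to want the answer. Exclusion 5.2.27 allows entry with QTcF up to 480 ms. Section 7.4 allows QT-prolonging drugs after Cycle 1 Day 1 to manage an emergent condition. Section 5.2.28 names hypokalemia as a risk factor for torsades, and in the phase I trial of this combination treatment-related hypokalemia was reported in 60% of 20 patients (Table 5). The main reassurance in section 2.1.4 is a nonclinical hERG result, and the ECGs in this trial are the patient-level check on it.

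**Working it through.** The plan states no figure on this point to reproduce. The check is whether the planned outputs can yield a patient-level result.

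**1. Amount of data.** Table 15 has 7 visits x 3 timepoints = 21 per sparse patient, of which 20 follow the Cycle 1 Day 1 pre-dose value.

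- At the protocol's planned 500 patients: (225 + 250) x 20 = 9,500 follow-up values if every visit is attended.
- At the 528 randomized patients in SAP 5.1.1, less 24 in the full set: 504 x 20 = 10,080, before any full-ECG values.

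Attendance at late cycles will be lower, so these are scheduled numbers, not expected ones.

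**2. Which output could give a count or a change?**

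| Output | Within-patient QTcF change | Patients over a limit |
|---|---|---|
| SAP 6.5 table | Not required | Not required |
| SAP 6.3.3 AE tables | No | Only events that investigators report; those ongoing at cut-off go to a separate table by term |
| Listings (SAP 5) | Not derived | Hand count at best, and tied to data that are in the tables |
| PK/PD exposure-response | Outside this SAP (6.4.2) | Outside this SAP; PK is sampled in Arm 1 only |

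SAP 6.3.4 and 6.3.5 refer PK and PRO to separate analysis plans. No such plan is cited for ECG.

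**3. What the continuous statistics pin down.** Suppose that at one timepoint the maximum is above 480 ms and the 75th percentile is below it. With the SAS default percentile definition:

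- n = 225: 0.75 x 225 = 168.75, so the 75th percentile is the 169th ordered value, and at most 225 - 169 = 56 patients lie above it. The count is anywhere from 1 to 56.
- n = 250: 0.75 x 250 = 187.5, the 188th value, so at most 250 - 188 = 62. The count is 1 to 62.

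If the 528 split evenly (264 per arm, so 264 - 24 = 240 sparse patients in Arm 1), the upper ends become 60 and 66. There the 75th percentile is the average of two adjacent ordered values, and 240 - 180 = 60 and 264 - 198 = 66.

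**4. Does using every statistic settle it?** No, but it narrows the range. The test was an integer search on a 1-ms grid with n = 225. It matched mean and SD to within 0.05 ms and quartiles, minimum and maximum exactly. All inputs here are assumptions, because the documents give no QTcF distribution.

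| Mean/SD (ms) | Q1/median/Q3 | Min-max | Patients > 480 ms that fit |
|---|---|---|---|
| 420/20 | 407/420/433 | 370-500 | 1 to 15 |
| 425/22 | 410/425/440 | 370-500 | 1 to 22 |
| 430/25 | 413/430/447 | 370-505 | 1 to 33 |

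Nor do such tables show whether the patients over 480 ms at one timepoint are the same ones at the next.

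**The case against.** **The absence cannot be proved.** SAP section 10 and the start of section 11 are not visible, nor is most of the contents page. The visible SAP also shows no laboratory or vital-sign analysis, so safety-measurement outputs may sit in the unseen text. This stands. A reader might infer that the trial has no plan to analyse QTc change at all; the documents do not support that. The condition in section 6.5 is visible, however, and needs attention whatever the unseen text holds.

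**ECG data need not mean raw values only.** The phrase does not exclude change or categories, section 5 has a rule for categorical data, and table shells could add both. This also stands, which is why the point is that the wording does not require these results, not that it rules them out.

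**No protocol commitment is broken.** The protocol says only that QTc is evaluated, and section 9.4.4 promises no change or threshold analysis. Correct: a reader might infer a contradiction between protocol and SAP, and there is none.

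**Other safeguards exist.** The full ECG set is centrally read and blinded, exposure-response on QTc is an exploratory objective, a DMC reviews unblinded safety data, and exclusions 5.2.28 and 5.2.29 keep out patients with added torsades risk or on QT-prolonging drugs at screening and Cycle 1 Day 1. These lower the risk to patients. None of them provides a between-arm summary of measured QTcF at patient level.

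**Some late cycles may be thin.** True, but a table that shows its n already tells the reader so.

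**Conclusion.** The concern holds in a limited form. QTc belongs to the secondary safety endpoint. The only ECG output in the visible SAP hangs on an undefined condition and, as worded, requires neither within-patient QTcF change nor a count of patients crossing a limit.

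The size of the gap is shown by the range of 1 to 56 of 225 patients at a single timepoint. That illustration uses the protocol's planned 500 patients and only the quartile and maximum. The narrower ranges that use all the statistics rest entirely on assumed distributions.

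None of this says that devimistat prolongs QTc or how often. No rate is assumed, and the documents give none. The 480 ms figure is the protocol's entry limit, not an analysis threshold that the plan has set.

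Severity is minor to moderate. The missing results are descriptive, and no tested endpoint, error rate or sample size is affected.

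**What to change.** In SAP 6.5:

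1. Delete the data-sufficiency condition for the cycles with scheduled ECGs (1, 2, 3, 6, 9 and 12).
2. In the safety population, tabulate by arm the QTcF change from baseline at each timepoint, with baseline as in SAP 5.6. The screening ECG then serves if the Cycle 1 Day 1 pre-dose value is missing.
3. Tabulate by arm the number of patients whose worst post-baseline QTcF exceeds 480 ms, or whose increase exceeds limits that the sponsor fixes before database lock. The documents give no increase limits; 30 and 60 ms would be one possible choice.
4. List those patients.
5. State that items 2 to 4 cover both the sparse and the full ECG sets.

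All of this is descriptive. The cost is two or three extra tables and one listing from data already collected, with no new ECGs and no protocol change. If the SAP text not visible here already holds these tables, a cross-reference in 6.5 and deletion of the condition are enough.
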